## I. Purpose, Background and Rationale

### A. Aim and Hypotheses

1. **Brief Introduction:** Despite widespread awareness of significant negative health consequences, cigarette smoking remains the leading cause of preventable morbidity and mortality in the US (Creamer et al., 2019; Jamal, 2018). Moreover, the highest rate of smoking and heaviest burden of smoking-related illness occurs among low-socioeconomic status (SES) individuals relative to higher SES groups (Businelle et al., 2010; Clegg et al., 2009). Low SES individuals are also 40% less likely to succeed in quitting smoking when they attempt to do so (National Center for Chronic Disease Prevention and Health Promotion (US) Office on Smoking and Health, 2014). One potential explanation for the disparity in rate of smoking and successful quit attempts may be differences in individual rates of delay discounting (DD), i.e., the degree to which rewards loses their value as the delays to their receipt increase (Odum, 2011). A proposed way to reduce steep DD and, potentially, substance use has been computer training for working memory, which has shown favorable results in a sample of individuals with stimulant dependence (Bickel et al., 2011) and substance use broadly (Felton et al., 2019), with the latter even showing decreases in cigarette smoking in a subset of the sample.
2. **Aims:** The current study will assess delay discounting (DD), working memory (WM) training, and cigarette smoking cessation outcomes. The aims of the project are the following:
  - Assess efficacy of WM training
    - Assess efficacy of WM training on cigarette smoking
    - Assess efficacy of WM training on DD

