## B. Background and Significance

1. Study Significance: The development of effective, theoretically coherent interventions addressing cigarette smoking is imperative, particularly interventions that would be feasible, efficacious, and acceptable in low-SES individuals. The proposed research is an innovative approach that capitalizes on previous findings showing reductions in delay discounting and even cigarette smoking. If working memory training is found to improve smoking cessation outcomes as a function of reductions in delay discounting, the project results could be helpful in future development of low-cost interventions for cigarette smoking.
2. The highest rate of smoking and heaviest burden of smoking-related illness occurs among low-SES individuals (Businelle et al., 2010; Clegg et al., 2009). One explanation for this disparity may be differences in individual rates of DD, which have been shown to be reduced with working memory training. (Bickel et al., 2011; Felton et al., 2019). Given the low cost of administering working memory training, such an intervention may be favorable for low-SES populations to improve smoking cessation outcomes.
3. Literature Review: DD has significant associations with:
  - **Cigarette smoking** (smokers tend to have higher rates of DD compared to non-smokers; Bickel et al., 1999);
  - **Smoking treatment outcome** (individuals who remained smoke free after a smoking cessation intervention had lower DD compared to those who didn't; González-Roz et al., 2019; Krishnan-Sarin et al., 2007; MacKillop & Kahler, 2009; Yoon et al., 2007);
  - **SES** (individuals with lower education and income have higher DD rates compared to those who are more educated and affluent; de Wit et al., 2007; Reimers et al., 2009).

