## C. Rationale

1. Although previous research has shown WM training to reduce DD, and cigarette use in a small subsample, the hypotheses of this study are largely exploratory. However, given the theoretical connections between DD, SES, and WM, it is expected that the hypotheses of this project will be supported.

2. The performance of this project may advance our knowledge of the relevant clinical targets for smoking cessation in low-SES individuals. In particular, this project is expected to shed light on DD as the putative mechanism in smoking for low-SES individuals and the durability of reductions in smoking as a result of reductions in DD through WM training.
3. Despite the evidence for some successful techniques for reducing DD, little of this work has been translated into intervention approaches to target clinical outcomes. This application seeks to capitalize on the emerging literatures indicating (1) WM training may be an effective and efficient way to reduce DD, and (2) DD is associated with SES, cigarette smoking, and treatment outcomes. Though WM training has been successfully implemented in laboratory-controlled experiments to reduce DD, we are not aware of any interventions for clinical disorders that specifically seek to do so and potentially enhance treatment outcomes.

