## II. Research Plan and Design

**A. Study Objectives:** The main aims of this project are to examine the observed efficacy of WM training.

**B. Study Type and Design:** This study is an open-label trial longitudinal (participants will be assessed through their 1-month quit date) trial.

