**C. Sample size, statistical methods, and power calculation**

1. Consistent with Stage 1a pilot trials, the current trial included a small sample size of completers ( $N = 15$ ) to determine the initial outcomes of the WM intervention and its perceived feasibility/acceptability.
2. DD will be estimated by fitting the hyperbolic function specified in Eq. 1 to the indifference points computed during the task in order to estimate each individual's discount rate, where  $v$  represents the discounted value of an outcome,  $V$  is the undiscounted value,  $D$  is the delay and  $k$  is the discounting parameter, which specifies the degree to which the value of a given reward is discounted when it is delayed (with higher values representing greater discounting).

$$v = \frac{V}{1 + kD}$$

Eq. 1

While  $k$  distributions tend to be skewed, post-hoc natural logarithmic transformations will be performed, which have been shown to approximate normal distributions. We will calculate  $k$  values for each magnitude (\$50, \$200, \$1000). Due to varying degrees of goodness-of-fit associated with nonlinear regression functions, we will also calculate area-under-the-curve (AUC) estimates (Borges et al., 2016). Hypotheses encompassed will be tested using Hierarchical Linear Modeling (HLM; Raudenbusch & Bryk, 2002), which allows the analysis of repeated measures and has been recommended because of its ability to: 1) accommodate missing data, 2) examine individual change over time in outcomes, and 3) include the average change and the individual variation around this average change which is especially important

in a small sample (Raudenbusch & Bryk, 2002; Singer. & Willett, 2003), even in smaller samples (Collado et al., 2019). Hypotheses encompassed within Aim 1 will be tested using Hierarchical Linear Modeling (HLM; Raudenbusch & Bryk, 2002), which allows the analysis of repeated measures and has been recommended because of its ability to: 1) accommodate missing data, 2) examine individual change over time in outcomes, and 3) include the average change and the individual variation around this average change which is especially important in a small sample (Raudenbusch & Bryk, 2002; Singer. & Willett, 2003), even in smaller samples (Collado et al., 2019).

3. Individuals who smoke cigarette and who are low in SES and receptive to a future quit attempt will be recruited for this study. Participants will be recruited from the greater Kansas City area.

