## **V. Data Analysis and Reporting**

**A. Statistical and Data Analysis:** Hypotheses encompassed within Aim 1 will be tested using Hierarchical Linear Modeling (HLM; Raudenbusch & Bryk, 2002), which allows the analysis of repeated measures and has been recommended because of its ability to: 1) accommodate missing data, 2) examine individual change over time in outcomes, and 3) include the average change and the individual variation around this average change which is especially important in a small sample (Raudenbusch & Bryk, 2002; Singer. & Willett, 2003), even in smaller samples (Collado et al., 2019).

- B. Outcome:** The study will conclude once we collect full data from 10 participants. It is expected that study hypotheses will be supported, with success/failure determined by results from WM training on cigarette use over time.
- C. Study results to participants:** Participants will be given information on their breath/saliva samples results immediately following testing if they are interested.
- D. Publication Plan:** Data will be used to support a subsequent NIH grant application. Attempts to publish in relevant peer-reviewed journal will made if hypotheses are sufficiently supported.

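### The success rule and smoking aim assign change in cigarette use to working memory training, but the plan has no allocated or modelled comparator and offers the same participants a quit date, a quitline and cessation groups

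*Combined protocol and SAP*

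**What the plan says.** **Success rule and aim.** V.B (Outcome) expects the hypotheses to be supported, "with success/failure determined by results from WM training on cigarette use over time". The aims in I.A include "Assess efficacy of WM training on cigarette smoking". The objective in II.A is to "examine the observed efficacy of WM training".

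**Design.** II.B: "This study is an open-label trial longitudinal". It names no arms and no allocation. Under Training sessions, Study Procedures describes a control program matched to the active one except for the memory demand, and speaks of active and control conditions. No section gives a ratio, a method of assignment or a number per arm.

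**Analysis.** II.C and V.A specify an HLM of average and individual change over time. Neither states a group term, a group-by-time term, an external benchmark, or a covariate for quit date or group attendance. V.B gives no contrast, threshold, test or alpha.

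**What else participants receive.**
- Interest in quitting is an entry criterion (II.D).
- Weekly behavioral cessation groups open after 5 of the 10 trainings, with rolling entry and attendance at will (Study Procedures; BA groups).
- At the post-training session everyone is asked to choose a quit date and is steered to the quitline.
- Two of the four smoking assessments are timed from the quit date.

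**Status.** I.C says "the hypotheses of this study are largely exploratory", and II.C justifies the sample this way: "Consistent with Stage 1a pilot trials, the current trial included a small sample size of completers".

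**The concern.** The rule names one component, WM training, as the source of the change to be judged. The schedule delivers that component together with other things intended to reduce smoking, to people chosen because they want to stop. Change over time in this group is the joint result of training, groups, quit attempt, quitline and prior motivation. Without a comparator in the model, no term isolates training.

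A favourable time trend could therefore be reported as WM efficacy when training did nothing. Section V.D says the data will support a further grant application and makes attempts to publish conditional on the hypotheses being sufficiently supported, so a wrong attribution would feed both decisions.

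**Working it through.** The plan gives no alpha, effect size, SD or false-success rate, so there is no figure to reproduce. The finding rests on step 1. Steps 2 to 4 only illustrate its possible size.

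**1. Can the rule be met with zero WM effect?** To separate training from the rest, the plan would need a concurrent control in the model, a benchmark, or smoking measured only before other cessation support begins.
- Control: described in Study Procedures, never allocated, absent from the HLM.
- Benchmark: none.
- Measurement before other support: not assured. Two of four assessments follow the quit date, and groups can start before the post-training visit.

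So yes, it can.

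**2. How a linear time term would treat a post-quit drop.** Assume a drop of X at the last two visits only. Slope = Σ(centred time × change) / Σ(centred time²).
- Visit number 0, 1, 2, 3: centred −1.5, −0.5, 0.5, 1.5; sum of squares 5. Slope = −X(0.5+1.5)/5 = −0.40X per visit. The fitted fall from baseline to post-training is 0.40X, where the true fall is zero.
- Assumed weeks 0, 5, 8, 11: centred −6, −1, 2, 5; sum of squares 66. Slope = −X(2+5)/66 = −0.106X per week. The fitted fall over 5 weeks is 0.53X.

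**3. How often a significant decline appears with zero WM effect.** Assumptions, none from the plan: cigarettes/day as outcome, mean 12, between-person SD 5, within-person SD 3, two-sided 5% t-test on per-person slopes, declines only counted, and a 25% mean post-quit reduction (X = 3/day). N is 10 (V.B) or 15 (II.C).

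*Same absolute cut for everyone (exact).* Slope SD = SD/√5 by visit number. With SD 3 this is 1.342, so the standardised slope is 0.40×3/1.342 = 0.894. At N=10 the noncentrality is 0.894×√10 = 2.83, and the chance of exceeding the critical t of 2.262 is 71% (68% with week coding). At N=15 it is 90% (87%). At N=10 with visit coding, SD 2 gives a standardised slope of 1.342 and 96%; SD 6 gives 0.447 and 24%.

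*Other response patterns (simulation, 20,000 runs per cell, range over the two time codings).*

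| Pattern, 25% mean reduction | N=10 | N=15 |
|---|---|---|
| Only a subset quits | about 16% | 30–31% |
| Half from quitters, half from cuts by the rest | 35–37% | 57–59% |
| Everyone cuts the same proportion | 63–66% | 83–86% |
| No change | about 2.5% | about 2.5% |

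A 10% reduction confined to quitters gives only 4.3% at N=10. None of these rates carries over to 7-day point prevalence, which the protocol also names as a smoking measure.

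**4. If a control does exist.** For standardised WM effects of 0.5, 0.8 and 1.0 SD, an even split gives power of about 12%, 24% and 35% (total 10) or 16%, 34% and 49% (total 15). Even 0.5 SD would need 63 per arm for 80% power. A group-by-time term at this size supports estimation, not an efficacy test.

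**5. Is baseline to post-training a pre-quit interval?** The post-training session asks for a quit date, which suggests so. But group Session 3 is placed one week before the quit date and schedules it, and Session 4 is the quit week. Groups are weekly and open after 5 trainings. The remaining 5 trainings at 2–3 per week take 5/3 to 5/2, or about 1.7 to 2.5 weeks, and the visit follows 2–3 days later. Starting promptly at Session 1 puts Session 3 two weeks on; rolling entry could bring it sooner. A quit date can therefore be scheduled, or reached, before the post-training visit.

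**The case against.** The strongest reply is that this is a Stage 1a pilot with hypotheses described as largely exploratory, an objective worded as observed efficacy, and training presented in II.D as an adjunct to group therapy. That stands as a defence of the design: an uncontrolled pilot of this size is legitimate. It does not cover a success-or-failure verdict tied to one component.

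Several stronger readings are tempting and should be resisted.
- *The rule counts any decline as a WM success.* It does not say so. Without a contrast or threshold the rule is undefined; what can be said is that it does not prevent misattribution.
- *There is no control.* The text on active and control conditions, and the fact that open-label does not by itself mean single-arm, make the documents contradictory on a comparator rather than plainly without one.
- *The background and rationale also attribute the effect.* I.B is conditional ("If working memory training is found to improve smoking cessation outcomes as a function of reductions in delay discounting"). I.C only expects the study to shed light on "durability of reductions in smoking as a result of reductions in DD through WM training". The aim and the success rule carry the point.
- *Baseline to post-training is a clean WM contrast.* In simulation a visit factor keeps that contrast at about 2.5%, but only because no pre-quit change was assumed. Group overlap and the conflicting quit-date text prevent that reading.

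The rates are also fairly open to challenge, since they move widely with the response pattern and the within-person SD.

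**Conclusion.** The point holds and should be corrected before the plan is used. The study's only stated success rule can be satisfied by a fall in smoking to which WM training contributed nothing, and no section guards against crediting it to training. This follows from the text and needs no simulation.

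The size is not known. Under the assumptions above, a significant decline with zero WM effect appears in about 15% to 70% of trials at N=10, depending on who responds and how. For equal 3/day cuts, within-person SDs of 6 to 2 widen this to about 24% to 96%, and small effects confined to a few quitters barely raise it above 2.5%. These figures show that the problem can be large; they do not estimate this trial's error rate.

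**What to change.** 1. **Settle the comparator.** Reconcile II.B with the control training in Study Procedures. If a control exists, state the allocation, add a group-by-time term to the HLM, and report it as an estimate with an interval given N of 10 to 15.
2. **If there is none, reword the aim in I.A and the rule in V.B.** For example: change in cigarette use from baseline will be reported as change over the combined program of WM training, behavioral groups, quit date and quitline, and will not be attributed to WM training.
3. **Reconcile the timing text.** Sessions 3 and 4 and the post-training session differ on when the quit date is set. II.D calls the training a pretreatment, while Study Procedures lets groups begin midway through it. Which schedule is intended is for the investigators to state.
4. **Optional.** Report change by visit. Record each participant's actual quit date and the groups attended before the post-training visit; attendance monitoring is stated for the computer trainings but not for the groups. Label baseline to post-training change as descriptive, and call it pre-quit only for participants whose quit date falls after that visit.

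Cost: a few sentences of protocol text and, for item 4, a short log. The claim becomes more modest, and modelling visit as a factor adds up to two time parameters in a small sample. If there is no control, no extra arm or participants are needed.

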4. Session 4 (quit week): Clinician will go over participants' use of the Daily Activity, Mood, and Smoking log, discuss quit dates and quitting experience (e.g., withdrawal and immediate plans) for each participant, discuss success in accomplishing LAVA activities, identify obstacles to abstinence, offer support, talk about maintaining a healthy lifestyle (i.e., proper diet and exercise), and highlight social support, particularly by encouraging participants to form a "Contract" with a supportive person in their life (i.e., ask someone to take part in an activity with them to help them remain abstinent, such as riding bicycles together).
5. Session 5: Clinician will go over participants' use of the Daily Activity, Mood, and Smoking log, participants' contracts, quitting experience (e.g., withdrawal symptoms), strategies to avoid smoking, perceived benefits and disadvantages to quitting smoking, and identifying high-risk situations.
6. Session 6: Clinician will go over participants' use of the Daily Activity, Mood, and Smoking log, quitting experience (e.g., withdrawal symptoms), strategies to avoid smoking, perceived benefits and disadvantages to quitting smoking, discuss time management as a tool for abstinence, help identify high-risk situations, and offer support.
7. Session 7: This session will mirror Session 6.
8. Session 8: This session will mirror Sessions 6 & 7, and will include a discussion on developing a post-program plan to maintain abstinence by engaging and monitoring activities after the BA group and dealing with negative feelings, triggers, and immediate cravings. The clinician will also review the overall program progress and remind participants about the upcoming follow-up sessions.

**Post-training session:** This session is expected to take 1 to 1.5 hours to complete. 2-3 days following their last training session, participants will complete the DD task, TLFB, TOH, HVLT-R, LNS, and provide a CO breath sample. Participants will be asked to set a quit date for their cigarette smoking at this session and will be encouraged to connect to the tobacco quitline ([name]).

**1-week post quit date session:** This session is expected to take about 30 minutes to complete. Around 7 days after their quit date, participants will complete the DD task, TLFB, and provide a CO breath sample. Participants will also provide a saliva sample to test for salivary cotinine, a metabolite of nicotine to biochemically verify smoking status/abstinence.

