## **Measures**

**SCID DSM-5.** If a participant reports frequent drug or alcohol use, they will fill out questionnaires on their DSM-5 symptoms for the respective substance (other than tobacco). Data will be recorded on Qualtrics, only identified by participant ID.

*Wide Range Achievement Test 4 (WRAT 4).* A reading survey to measure participant's grade-level equivalent reading ability. This will be administered at the baseline session. Data will be recorded on paper, only identified by participant ID.

*Single Commodity Delay Discounting (DD).* A binary choice procedure will be conducted on a personal computer to assess DD. On each DD trial, two hypothetical money rewards will be presented on the screen. One outcome will be an amount of money available immediately; the other outcome will be a larger amount of money (\$50, \$1,000) available after some specified delay (1 week, 1 month, 6 months, 1 year, 5 years). Participants will indicate the preferred alternative with a mouse-click, and the computerized algorithm (Holt et al., 2003) will adjust the immediate reward over 6 trials to determine an indifference point for each amount/delay pairing, resulting in 7 indifference points (corresponding to the 7 delays) for each of 2 amounts (\$50\$1,000). Indifference points will be used to calculate delay discounting rates. Participants will be told to indicate preference on the task as if the outcomes were for real money; previous research has established the validity and reliability of DD tasks for hypothetical rewards (Matusiewicz et al., 2013). The results of this assessment will be recorded on a laptop computer, only identified by participant ID.

*Timeline Follow-Back (TLFB; Sobell & Sobell, 1992).* A 7-day TLFB methodology will be employed to assess point prevalence of tobacco use. Participants will be asked to report number of cigarettes smoked for each day. Participants will also be asked to report nicotine vape and marijuana use. Data will be recorded on Qualtrics, only identified by participant ID.

*Tower of Hanoi (ToH).* This assessment consists of a board with 3 pegs and 4 disks of differing sizes. Participants must move the stack of disks from one peg to another while following specific rules (i.e., all pegs must end up on the farthest peg and at no point can a larger disk be placed on top of a smaller disk). Task will be completed with a research assistant and data will be recorded on Qualtrics, only identified by participant ID.

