*Hopkins Verbal Learning Test – Revised (HVLT-R; Brandt & Benedict, 2001).* This standardized assessment of verbal learning and memory requires participants to memorize a list of words presented auditorily. Participants are then asked to recall or recognize as many words as possible, either immediately or following a delay. Task will be completed with a research assistant and data will be recorded on Qualtrics, only identified by participant ID.

*Letter Number Sequencing (LNS).* This measure of working memory is in the Adult Intelligence Scales–III (Wechsler, 1997). The participant is given a mixed string of letters and numbers that they must then put into a sequential order of numbers followed by a sequential order of letters. The string presentation increases in difficulty until the participant is no longer able to correctly sequence three strings of equivalent difficulty. Task will be completed with a research assistant and data will be recorded on Qualtrics, only identified by participant ID.

*Fagerstrom Test for Nicotine Dependence (FTND; Heatherton et al., 1991).* Nicotine dependence will be measured using the 6-item FTND, a standard instrument for assessing intensity of physical addiction to nicotine as it relates to smoking. Data will be recorded on Qualtrics, only identified by participant ID.

*Expired Breath Carbon Monoxide (CO).* Smoking status will be measured with an expired carbon monoxide (CO) level using a coVita Micro+basic Smokerlyzer monitor (<https://www.covita.net/product/microbasic-smokerlyzer/>). A CO level below 9 parts per million will indicate smoking abstinence for 12 hours or less. Trained research staff will administer this measure. Disposable mouthpieces will be used for each individual, and the results will be shared with the participants immediately following completion if they are interested. Data will be recorded on the CO monitor and on Qualtrics, only identified by participant ID.

*Salivary Cotinine.* Smoking status will also be measured with a salivary cotinine measure (saliva sample) using NicConfirm mouth swab cotinine tests (<https://www.confirmbiosciences.com/products/retail-brands/nicconfirm-swab-cotinine-test/>). A cotinine level below 30 ng/ml will indicate smoking abstinence for 1 week or less. The results will be shared with the participants immediately following completion if they

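### Publication is made conditional on the hypotheses being supported, and the success/failure verdict names no deciding smoking variable or model contrast

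*Combined protocol and SAP*

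**What the plan says.** Three statements in Section V (Data Analysis and Reporting) bear on this.

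- V.B states an expectation, "It is expected that study hypotheses will be supported", and then the decision rule, "success/failure determined by results from WM training on cigarette use over time".
- V.D sets the publication rule: "Attempts to publish in relevant peer-reviewed journal will made if hypotheses are sufficiently supported". It also commits the data to a later grant application, without any condition.
- V.A names hierarchical linear modelling (HLM) for the Aim 1 hypotheses. It gives no dependent variable, time coding, contrast or significance level.

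The matching aim in Section I.A is equally general: "Assess efficacy of WM training on cigarette smoking".

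The Measures section supplies several ways to read smoking. One instrument yields both a daily count and a point prevalence: "A 7-day TLFB methodology will be employed to assess point prevalence of tobacco use. Participants will be asked to report number of cigarettes smoked for" every day. Two biochemical tests carry person-level cut-offs: "A CO level below 9 parts per million will indicate smoking abstinence for 12 hours or less", and "A cotinine level below 30 ng/ml will indicate smoking abstinence for 1 week or less".

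**The concern.** The two rules reinforce each other. V.B announces pass or fail on a quantity that is not pinned down, and V.D makes submission depend on whether the hypotheses are sufficiently supported, a phrase that is also undefined. An analyst who follows the plan to the letter can decide, with the data in hand, whether the cigarette count or CO is the deciding reading, and which contrast counts as change over time. If nothing looks supportive, the plan says in effect not to submit.

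The publication rule is the more serious half. It is a stated rule, not an omission, and its direct product is selective reporting. The unnamed outcome in V.B, taken alone, would be close to ordinary missing detail in a small exploratory pilot. It matters here because a verdict and a publication decision rest on it.

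**Working it through.** The plan gives no alpha, power, effect size or success threshold, so there is no figure of its own to reproduce. The check is first textual, then a small calculation under stated assumptions.

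**Step 1. Is there a trial-level criterion anywhere?** The CO cut-off (below 9 ppm) and the cotinine cut-off (below 30 ng/ml) classify a person. Nothing says how they combine with the Timeline Followback (TLFB), how many abstainers would be a success, or how large a reduction would be. So person-level thresholds exist and a trial-level one does not.

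**Step 2. Which readings could realistically compete as change over time under HLM?** The wording of V.B and the choice of HLM imply one repeated-measures model per outcome, not one test per visit.

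- TLFB cigarette count: collected at baseline and at all three later assessments. Continuous trend; counts.
- Expired CO in ppm: same schedule. At the post-training session, for instance, "participants will complete the DD task, TLFB, TOH, HVLT-R, LNS, and provide a CO breath sample". Continuous trend; counts.
- CO below 9 ppm: the same breath sample dichotomised, so not a further reading.
- Cotinine: no baseline saliva sample in the baseline session text or in the Timeline table, so change from baseline cannot be tested.
- TLFB 7-day point prevalence: binary. Entry requires at least four cigarettes a day for at least 6 months, so baseline abstinence should be essentially zero. With no true change there would be almost no abstainers later. An exact paired test needs at least six changes, all in one direction, to reach 5% (2 × 0.5^5 = 0.0625; 2 × 0.5^6 = 0.031). With 15 completers (Section II.C) or 10 (Section V.B), it would almost never reject by chance.

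That leaves two continuous trends.

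**Step 3. Chance of at least one spurious result from two trends.** Assumptions: two-sided 5% per test, no true change, bivariate normal test statistics with correlation ρ.

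If independent:
- either direction: 1 − 0.95² = 0.0975
- favourable direction only: 1 − 0.975² = 0.0494

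For ρ > 0, the chance is 1 − P(|Z1| < 1.96 and |Z2| < 1.96), or 1 − P(Z1 < 1.96 and Z2 < 1.96) for favourable results only:

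| ρ | Either direction | Favourable only |
|---|---|---|
| 0 | 9.8% | 4.9% |
| 0.6 | 8.8% | 4.4% |
| 0.8 | 7.8% | 3.9% |
| 0.9 | 7.0% | 3.5% |
| One pre-specified test | 5.0% | 2.5% |

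These figures cover the choice of variable only. The choice of contrast within a model is also open and is not quantified here.

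**The case against.** The best defence is the study's stage. Section II.C calls it a Stage 1a pilot, and Section I.C describes its hypotheses as largely exploratory. Such a study needs neither a powered test nor a confirmatory endpoint. That stands, and nothing here asks for one. It does not excuse a pass/fail verdict or a results-dependent publication rule, which sit badly with an exploratory purpose.

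The defence can also say that CO and cotinine are described in Section II.E as means of confirming abstinence, not as rival outcomes, and that the plan already points to a trend. Both are fair. They are why the inflation is small, but they still leave the dependent variable and contrast unnamed.

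Section IV.D counts data retention from publication of the primary results, which presumes publication. This softens the inference that null results would stay unpublished, but does not remove the V.D condition.

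Three stronger readings are tempting, and the documents do not support them:

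- A reader might count five smoking readings at two post-quit visits, ten in all, and infer a false-positive chance of 1 − 0.95^10 = 40%, or about 25% at correlation 0.6. That treats each visit as a separate test, counts CO twice, includes cotinine without a baseline, and gives binary readings a full 5% error rate that they would not have.
- A reader might infer that the grant evidence is biased upward by unpublished null results. V.D commits the data to the application unconditionally, and only journal submission carries a condition.
- A reader might infer that publication depends on the smoking result alone. V.D refers to hypotheses in general, and the aims also cover delay discounting.

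**Conclusion.** The point holds in a limited form. V.D conditions publication on the results, and V.B declares success or failure without naming the deciding smoking variable or contrast. Followed as written, unsupportive results would not be submitted, and the deciding reading could be selected after the data are seen.

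The added false-positive risk from choosing between the two continuous trends is modest: about 2 to 5 percentage points above a single two-sided test, or about 1 to 2.5 points in the favourable direction. This rests on an assumed alpha of 5%, assumed correlations from 0 to 0.9, and the reading that V.B means one trend per outcome. The objection to V.D rests on none of these assumptions; it follows from the sentence itself and is the main reason to amend.

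**What to change.** **V.D:** replace the condition with a commitment to report the results whatever their direction.

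**V.B:** before analysis, name one deciding smoking outcome and one HLM contrast that fits the plan's own idea of change over time. Change in TLFB cigarettes per day from baseline to 1 month post-quit is one example. Report its estimate and interval in place of a success/failure verdict, and label the other smoking, delay discounting and working memory readings exploratory. A verified-abstinence endpoint is not required; it would replace the plan's quantity with a different one.

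**Cost:** wording in two paragraphs, with no new data, visits or participants. The study team loses some freedom to highlight other readings.
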